Study protocol and statistical analysis plan

Evaluation of the course and effectiveness of conservative therapy in patients with Achilles tendinopathy

NCT number: NCT05702918

Date: March 28, 2022

(Date of approval of the project by the ethics committee)

Study design and description

This work is designed as a randomized clinical trial, in which the effects of a protocol of 12-week resistance training loading the Achilles tendon and low-energy focused extracorporeal shock wave therapy (ESWT) in patients with Achilles tendinopathy (AT) will be monitored. It is estimated that at least 40 patients will participate, randomly divided into two groups. Group A will be instructed to perform a training protocol in combination with ESWT according to selected parameters. Group B only completes the same training protocol.

The research within one patient will last a total of 26 weeks from the initial to the final examination and will include several control measurements: at 6, 12, and 26 week from the beginning of therapy. Potential participants will be selected based on the recommendation of a specialist doctor and their suitability will be assessed according to the inclusion criteria. They will then be invited to an initial examination. This will include an objective examination by a physiotherapist, a subjective assessment by the patient and an ultrasonographic (USG) examination followed by a micromorphological analysis using special software. At the end of the initial examination, the participant will be randomly assigned to group A or B. Group A will follow resistance training protocol and receive ESWT. Group B will follow resistance training only. The study program for a specific participant will depend on the assigned group.

Patient selection

Inclusion criteria: age 18–50 years; localized Achilles tendon pain limiting daily or sports activity; clinical manifestation of AT confirmed by a clinician; and unilateral symptoms.

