Exclusion criteria: professional or high-volume recreational sports (>4 sessions/week, >1h each); contraindications to ESWT according to International Society for Medical Shockwave Treatment (ISMST) guidelines at <https://shockwavetherapy.org>; previous symptomatic mechanical tendon injury (partial/complete rupture); history of contralateral AT; neurological, metabolic, oncologic, or systemic disease (e.g., diabetes, neuropathy, lupus, spondyloarthritis, rheumatoid arthritis); AT-specific treatment within the past 6 months; or use of anticoagulants or statins.

Initial and final examination

During the initial and final examinations, the several tasks to the patient will be performed. Firstly the anamnestic data will be collected, then the area of greatest pain will be localized by palpation.

Secondly, the patient will be asked to complete a validated Victorian Institute of Sports Assessment - Achilles (VISA-A) questionnaire, which assesses the subjectively perceived severity of the disease and partly its impact on the quality of normal daily or sports activities.

The patient's maximal pain will be assessed using a standardized numerical rating scale (NRS) of pain. The patient will be asked about the morning and maximum pain that could be caused by various factors.

Lastly, the ultrasonographic (US) examination and subsequent software analysis using Spatial Frequency Analysis (SFA) of patient's AT in both legs will be performed. This examination is described in the following chapter.

Both, initial and final examinations in each patient will be performed by only one person (the investigator of the study).

Ultrasonographic examination

Ultrasound imaging will be performed by the same experienced examiner using a linear probe (L12-3E, 12 MHz) on a Mindray DC-70 system in MSK preset (B-mode). The participant will be placed in the prone position with the knee in an extended position and the ankle passively maintained in neutral position. The midportion of the Achilles tendon will be evaluated from the

myotendinous junction to the upper border of calcaneus. The probe will be placed as parallel to the tendon fibers as possible, and the image capture will be always carefully performed to ensure optimal image quality and minimize movement artifacts.

The values of anteroposterior tendon width at the anteroposterior widest point will be collected using the measuring instruments included in USG machine.

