After that, the preset will be changed to the specific setting, and three pictures will be saved in long axis for subsequent micromorphological analysis using SFA. SFA is a non-invasive, specialized method which analyzes the US image *in vivo*. In particular, it analyzes the anisotropic B-mode speckle pattern arising from within a tissue type in the spatial frequency domain and is capable of detecting and comparing collagen fascicles organization, spacing, and density across various parameters. Mean of those three values will be used for statistical analysis.

ESWT application

The low-energy focused ESWT will be applied using the BTL-6000 FSWT machine with piezoelectric generator and a coupling pad which modulates penetration depth to 0-35 mm. The setting is chosen based on ISMST guidelines (<https://shockwavetherapy.org>): Energy Flux Density (EFD) between 0.10-0.15 mJ/mm² due to patient tolerance, frequency at 5 Hz. A total of 2000 shocks will be applied semi-statically to the most US defined pathological tendon area using a contact gel. The set parameters will not change during the study and will remain the same for each patient.

Data analysis

The normality of the data distribution will be determined by calculating the Shapiro-Wilk p value. Independent t-tests (or Mann Whitney U tests for non-parametric) will be performed for each parameter to compare baseline values between groups. In addition, paired t-tests (or Wilcoxon tests) will be performed for each parameter, evaluated in each group separately between baseline and final values. To reach effect size, Cohen's d will be calculated for paired t-tests and biserial rank correlation for non-parametric Wilcoxon test.

Intergroup statistical significance between baseline and follow-up values of morphological parameters will be evaluated using two-way ANOVA with repeated measures or non-parametric Friedman test. Statistical significance is set to $p < .05$.

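### The only post-baseline comparison between arms is limited to morphological parameters, so the planned analysis cannot say whether adding ESWT improves VISA-A or pain

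*Combined protocol and SAP*

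**What the plan says.** The Study design and description section sets the randomised contrast: "Group A will follow resistance training protocol and receive ESWT. Group B will follow resistance training only". The Initial and final examination section collects two kinds of patient-reported outcome at both examinations. One is VISA-A, "which assesses the subjectively perceived severity of the disease and partly its impact on the quality of normal daily or sports activities". The other is NRS pain, asked as morning and as maximum pain. Ultrasound supplies tendon width and the SFA parameters.

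The Data analysis section then plans three sets of tests:

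1. Independent t or Mann-Whitney tests between the arms for every parameter, on baseline values only.
2. Within-arm tests for every parameter: "paired t-tests (or Wilcoxon tests) will be performed for each parameter, evaluated in each group separately between baseline and final values". Effect sizes are attached to this set alone: "Cohen's d will be calculated for paired t-tests", with a rank-based counterpart for the Wilcoxon test.
3. One comparison of the arms over time, by two-way repeated-measures ANOVA or the Friedman test: "Intergroup statistical significance between baseline and follow-up values of morphological parameters will be evaluated".

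No other section plans a comparison of VISA-A or pain between the arms after baseline.

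**The concern.** A questionnaire score and a pain rating are not morphological parameters. The section refers to every parameter in the first two sets of tests and narrows the scope only in the third, so on its face the restriction is deliberate. The symptom outcomes are therefore left with a baseline comparison, which precedes treatment, and two separate before/after results.

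Those before/after results cannot isolate ESWT. Both arms do the same training, so both may improve through loading, natural course or regression to the mean. The ESWT effect is the difference between the arms, and the plan neither tests nor estimates it for symptoms. A reader who wants an answer can only compare two p-values or two paired effect sizes, which gives up the protection of randomisation for these outcomes. Patients enter because tendon pain limits their activity, and the title speaks of effectiveness, so the unanswered question is central to the trial.

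**Working it through.** **Coverage of the plan, by outcome**

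| Outcome | A vs B at baseline | Before/after within each arm | A vs B after baseline |
|---|---|---|---|
| Tendon width, SFA | yes | yes | yes (ANOVA or Friedman) |
| VISA-A | yes | yes | none |
| NRS, morning and maximum | yes | yes | none |

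The finding rests on this table. The arithmetic below shows only how badly the within-arm tests would serve as a substitute.

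**Inputs.** The total sample is from the Study design and description section: "It is estimated that at least 40 patients will participate, randomly divided into two groups". No allocation ratio, power, effect size, SD or dropout is given, so there is no sample-size calculation to reproduce. Assumptions: 20 per arm (40/2), no dropout, and two-sided testing at the stated 0.05. The standardised within-arm change, dz = mean change / SD of change, is also assumed and is varied over a range.

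**No ESWT effect (same dz in both arms).** The power p of a paired t-test comes from the noncentral t with 19 df and noncentrality dz × √20. The arms are independent, so P(exactly one significant) = 2p(1 − p).

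| dz | p | 2p(1 − p) |
|---|---|---|
| 0.2 | 0.136 | 23% |
| 0.3 | 0.247 | 37% |
| 0.46 | 0.497 | 50% |
| 0.6 | 0.721 | 40% |
| 0.8 | 0.924 | 14% |
| 1.0 | 0.989 | 2.3% |
| 1.2 | 0.999 | 0.2% |

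For example, at dz = 0.3: 2 × 0.247 × 0.753 = 0.372. In half of these discordant results A is the significant arm, which would read as a benefit of ESWT. A valid test would give a false difference 5% of the time.

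**Real ESWT effect.** With dz = 1.2 in A and 0.8 in B, P(both significant) = 0.999 × 0.924 = 0.92. With 1.8 and 1.0 it is about 0.99. In both cases the paired tests report improvement in each arm and do not reveal the difference.

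**What a direct comparison would deliver.** For a two-sample t-test of change with 20 per arm, use the noncentral t with 38 df and noncentrality d × √10:

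- d = 0.4 (the 1.2 versus 0.8 case, equal SDs): power about 23%
- d = 0.5: 34%
- d = 0.8: 69%
- 80% power is reached at about d = 0.91.

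The 95% CI half-width is roughly 2.02 × √(2/20) = 0.64 SD of change. Baseline adjustment may narrow this, but the documents give no correlation from which to say by how much.

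**The case against.** The strongest case on the other side accepts the gap and disputes its size.

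- **The false-signal rate depends on dz.** It runs from nearly 0% to 50%. If training alone produces large changes (dz of 1.0 or more), a discordant result is rarer than 5%. This stands: the figures are conditional illustrations. When changes are large, however, the failure is the opposite one, with both arms significant and any difference hidden.
- **The plan never says that ESWT's effect on symptoms will be read from the two within-arm results.** True. The defect is an omission, and the percentages describe an inference that the plan leaves open. The title also covers the course of therapy, which paired tests can fairly describe. They do not address effectiveness.
- **The data are not lost.** Both outcomes are collected in both arms, so the limitation belongs to the written analysis and not to the trial. That makes the repair cheap, but it still has to be specified before outcomes are compared, or the symptom result becomes post hoc.
- **No primary outcome is named, and morphology may be the main interest.** The documents do not rank symptoms below morphology, and they plan significance tests and effect sizes for them, so this does not excuse the gap.
- **The added comparison will have low power.** This stands, and it is a reason to report an estimate with its interval instead of relying on a p-value.

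**Conclusion.** The concern holds, and the plan should be corrected before outcomes are analysed. Followed as written, it yields no valid statement about ESWT's effect on VISA-A or pain. That conclusion comes from the text and needs no numerical assumption. How far the within-arm tests would mislead does depend on assumptions (20 per arm, two-sided 0.05, no dropout, assumed dz). With no ESWT effect, the chance that exactly one arm is significant peaks at 50% near dz = 0.46 and falls to 0.2% at dz = 1.2. With a real difference of 1.2 versus 0.8, the tests conceal it 92% of the time. Correcting the plan gives a valid estimate, but about 40 patients will reliably detect only a large difference.

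**What to change.** In the Data analysis section, extend the comparison of the arms to all outcomes:

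- For VISA-A, morning NRS and maximal NRS, estimate the A minus B difference at week 26, adjusted for the baseline value (ANCOVA, or an equivalent mixed model). Do the same at week 12 where these are measured; the protocol lists a week 12 control but does not say what it includes.
- Report each difference with a 95% CI and a standardised between-group effect size.
- Label the within-arm paired tests and their effect sizes descriptive, and state that no conclusion about ESWT will be drawn from them.
- Do not carry the Friedman fallback over to these outcomes. It has no group factor, so it would not compare the arms; the same problem affects the morphological parameters if that fallback is used.
- State the expected precision, so that a wide interval is not read as evidence of no effect.

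The cost is a change of SAP wording and a few extra model runs. No new measurements or patients are needed.

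### The non-parametric option for the intergroup analysis of the morphological parameters is the Friedman test, which has no group factor and cannot compare the arms

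*Combined protocol and SAP*

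**What the plan says.** The Data analysis section plans three sets of tests.

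1. Independent t-tests or Mann-Whitney U tests "will be performed for each parameter to compare baseline values between groups".
2. Paired t-tests or Wilcoxon tests, "evaluated in each group separately between baseline and final values".
3. For "Intergroup statistical significance between baseline and follow-up values of morphological parameters", a two-way repeated-measures ANOVA or, as the non-parametric option, the Friedman test: "values of morphological parameters will be evaluated using two-way ANOVA with repeated measures or non-parametric Friedman test".

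On distribution, the section says that "The normality of the data distribution will be determined by calculating the Shapiro-Wilk p value". It gives no cut-off and does not say whether raw values, changes or residuals are tested.

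The visits are described in two ways. Study design and description "will include several control measurements: at 6, 12, and 26 week from the beginning of therapy". The examination section, which contains the ultrasound step, is worded for two occasions: "During the initial and final examinations, the several tasks to the patient will be performed". The number of imaging visits that enter the analysis is therefore not settled.

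The morphological parameters are not defined. I read them as tendon width and the SFA values; the point does not depend on that reading.

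**The concern.** The third set of tests is labelled intergroup, but one of its two options cannot answer an intergroup question. Friedman treats each patient as a block and ranks that patient's visits. Which arm the patient is in does not enter the statistic. Nor can the arms serve as the Friedman conditions, because every block must be measured under every condition and the arms contain different, unmatched patients.

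The consequence is serious in this design because the training is common to both arms ("Group B only completes the same training protocol"). Change shared by both arms is plausible, and that is what a pooled Friedman test detects. If the test is run arm by arm instead, it invites reading significance in one arm only as an effect of ESWT. Either way, a p-value reported as intergroup could be taken for evidence on ESWT when it is not. This is also the only planned comparison of the arms after baseline for any outcome.

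**Working it through.** **Step 1: which planned tests compare the arms after baseline?**

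| Planned test | Group factor? | Uses follow-up? |
|---|---|---|
| Independent t / Mann-Whitney U | yes | no, baseline only |
| Paired t / Wilcoxon | no, within each arm | yes |
| Two-way repeated-measures ANOVA | yes, through group-by-time | yes |
| Friedman | no | yes |

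On the non-parametric path no row has yes in both columns.

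**Step 2: relabelling.** If Friedman compared the arms, reassigning patients between arms would change its p-value. In one simulated four-visit data set with 1,000 random reassignments, the Friedman p-value was .013 every time. The Mann-Whitney p-value on change ranged from .003 to 1.0.

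**Step 3: inputs for size.** The plan expects at least 40 patients in two groups. It gives no allocation ratio, SD, correlation or expected change, and there is no calculation of its own to reproduce. Assumed: 20 per arm, normal data, within-patient correlation ρ = 0.5 (0.8 as sensitivity), changes in SD units, two-sided 5%. All rates are conditional on Friedman being used.

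**Step 4: two visits, exact.** With two visits Friedman reduces to a sign test. If c of n patients increase, χ² = (2c − n)²/n on 1 df, with critical value 3.84.

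- n = 40: c = 27 gives 14²/40 = 4.9 and c = 26 gives 12²/40 = 3.6, so it rejects at c ≥ 27 or c ≤ 13.
- n = 20: c = 15 gives 10²/20 = 5.0 and c = 14 gives 8²/20 = 3.2, so it rejects at c ≥ 15 or c ≤ 5.

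A patient with mean change d increases with probability p = Φ(d/√(2(1 − ρ))). At ρ = 0.5 the divisor is 1, so d = 0.3 gives p = Φ(0.3) = 0.618. Binomial tails then give, with **no ESWT effect**:

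| Shared change (SD) | 0 | 0.2 | 0.3 | 0.5 | 0.8 |
|---|---|---|---|---|---|
| Pooled Friedman rejects, ρ 0.5 | .038 | .144 | .284 | .661 | .969 |
| Pooled Friedman rejects, ρ 0.8 | .038 | .312 | .614 | .966 | 1.00 |
| One arm rejects (r), ρ 0.5 | .041 | .094 | .163 | .384 | .764 |
| Exactly one arm significant, 2r(1 − r), ρ 0.5 | .079 | .170 | .273 | .473 | .361 |
| Exactly one arm significant, ρ 0.8 | .079 | .292 | .456 | .371 | .025 |

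**Step 5: can the p-value tell an effect from shared change?** Two visits, ρ = 0.5, convolving the two arms' binomials:

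| Scenario | Pooled Friedman | Mann-Whitney on change (simulated) |
|---|---|---|
| A +0.8, B +0.3 (real difference) | .721 | .325 |
| Both +0.55 (no difference) | .745 | .049 |

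Friedman rejects slightly more often where there is no difference. With A +0.5 and B −0.5, a difference of a full SD, pooled Friedman rejects in only .025 of trials.

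**Step 6: four visits, simulated (20,000 trials, ρ = 0.5).**

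| Course over the four visits (SD) | Pooled Friedman | Mann-Whitney on change | ANOVA group-by-time |
|---|---|---|---|
| Shared 0/0.1/0.2/0.2 | .162 | .051 | .050 |
| Shared 0/0.3/0.5/0.5 | .755 | .049 | .051 |
| A 0/0.4/0.8/0.8, B 0/0.15/0.3/0.3 | .824 | .316 | .297 |
| Shared 0/0.275/0.55/0.55 | .848 | .048 | .047 |

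At ρ = 0.8 the first two Friedman rates become .367 and .993. Run by arm in the second scenario, exactly one arm is significant in .483 of trials.

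**Step 7: skewed data.** The option is meant for non-normal data, so a separate four-visit simulation used exponential errors (3,000 trials per scenario, linear change over the visits, total change in units of the error SD).

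| Total change A, B | Pooled Friedman | Mann-Whitney on change |
|---|---|---|
| 0, 0 | .049 | .051 |
| +1, +1 | .998 | .047 |
| +1, −1 | .017 | .996 |
| +1.5, +0.5 | .996 | .701 |

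The pattern is the same.

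**The case against.** The strongest reply is that the fault is conditional. ANOVA is named first and can carry a group-by-time term, and the plan does not show that the Friedman option will ever be used. No primary outcome is named, so it is not established that the morphological parameters carry the main conclusion. This is a fair limit on the reach of the finding. It does not repair the option: with no cut-off and no tested quantity for Shapiro-Wilk, its use cannot be ruled out for any parameter. An analyst who turned to Mann-Whitney on change instead would be leaving the plan, which reserves that test for baseline.

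The rates are also open to criticism. They are illustrations, mostly on normal data. The two-visit case is a less natural use of Friedman, since the plan already names Wilcoxon for baseline against final. One-arm-only significance is common at moderate shared change but not everywhere: 2.5% at 0.8 SD with correlation 0.8. All of this stands, and the percentages are not this trial's error rates. The four-visit and skewed-data results lead to the same conclusion, which rests on the form of the test.

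Finally, calling the ANOVA route sound assumes that its factors are group and time. The plan does not name them, and both legs are imaged, so leg could be a factor.

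**Conclusion.** The concern holds, and the option is wrong as written. Where Friedman is used, the randomised comparison for that parameter is left untested. The structural conclusion needs no numerical assumption.

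Its size does. With 20 per arm and correlation 0.5, shared changes of 0.2 to 0.8 SD and no ESWT effect give pooled rejection in 14% to 97% of trials with two visits, and 16% to about 75% for the two four-visit courses ending at 0.2 and 0.5 SD. A between-arm test on change stays near 5% throughout. How often the option will be used cannot be estimated from the documents.

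This should be corrected before analysis, because the sentence holds the plan's only comparison of the arms after baseline.

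**What to change.** Remove Friedman from the intergroup analysis and prespecify one fallback that keeps the group factor. For example:

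> *If the non-parametric option is used, the groups will be compared by a Mann-Whitney U test on the change from baseline to week 26, using one prespecified value per patient, with the Hodges-Lehmann estimate and 95% CI.*

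The value per patient needs naming (symptomatic tendon or side-to-side difference). Two tendons from one patient are not independent observations. If images are taken at weeks 6 and 12 and are to be used, a rank-based or permutation test of group-by-time is the alternative. In simulation (4,000 trials, 499 permutations, correlation 0.5) the permutation test rejected .047 under the shared course 0/0.3/0.5/0.5 SD and .303 under the real effect in Step 6.

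The section should also state:

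- what triggers the fallback: the quantity tested and the cut-off;
- at which visits ultrasound is done and analysed;
- that the ANOVA factors are group and time, with group-by-time as the term of interest.

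VISA-A and pain have no planned between-arm comparison after baseline on either route. Correcting this sentence alone leaves that gap open, so it should be closed in the same revision.

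For the morphological parameters the cost is a few lines of text, standard software and no new data. The small drawback is that a week-26 change test does not use any intermediate images.

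### The follow-up analyses need complete values from every patient and the plan has no missing-data method, so a patient without a week-26 value is lost (and one missing week 6 or 12 too, if those visits enter the ANOVA)

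*Combined protocol and SAP*

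**What the plan says.** Under Study design and description, follow-up lasts 26 weeks and "will include several control measurements: at 6, 12, and 26 week from the beginning of therapy". On numbers, "It is estimated that at least 40 patients will participate, randomly divided into two groups".

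The Data analysis section names two kinds of follow-up analysis:

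- Within arms: "paired t-tests (or Wilcoxon tests) will be performed for each parameter, evaluated in each group separately between baseline and final values".
- Between arms: the comparison of morphological values at baseline and follow-up "will be evaluated using two-way ANOVA with repeated measures or non-parametric Friedman test". This sentence covers morphological parameters only and does not list the visits that enter.

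The section on the initial and final examination describes VISA-A, pain rating and ultrasound with SFA at those two examinations. No section says what is measured at weeks 6 and 12. Nothing in the document defines an analysis population, a rule for withdrawals or missed visits, imputation, a likelihood-based model, a sensitivity analysis or an expected dropout rate.

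**The concern.** The paired t-test and the Wilcoxon test need both values of a pair. Classical repeated-measures ANOVA and the Friedman test need every time point that enters. With no other rule stated, the usual consequence is that an incomplete patient is removed whole, including the visits attended.

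Two things are at stake. First, the randomised comparison of morphology becomes a comparison of those who stayed; if patients doing badly leave one arm more often, that arm looks better without any treatment effect. Second, even if loss is unrelated to outcome, a trial of about 40 gives up data it has collected. The exposure is real: follow-up runs 26 − 12 = 14 weeks beyond the training programme, the arms receive different treatment, and no sham is described for Group B. Whether loss will in fact differ by arm cannot be known from the document.

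**Working it through.** **Inputs.** From the document: at least 40 patients, two arms, baseline plus weeks 6, 12 and 26. The figure of 40 has no effect size, SD, power or dropout behind it, so it cannot be reproduced. Assumed: 20 per arm, unit SD at each visit, equal correlation 0.6 between visits, no true effect, and the loss rates below.

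**1. Patients retained.** If each follow-up visit is missed independently with probability m, the fraction kept is (1 − m)³ when all three follow-up visits enter, and 1 − m when only the final one does.

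| m | (1 − m)³ | of 40, all visits | of 40, baseline and final |
|---|---|---|---|
| 5% | 0.857 | 34.3 | 38 |
| 10% | 0.729 | 29.2 | 36 |
| 15% | 0.614 | 24.6 | 34 |
| 20% | 0.512 | 20.5 | 32 |

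**2. Precision at m = 10%.** The SD of a baseline-to-week-26 change is √(2 × (1 − 0.6)) = 0.894. The standard error of the arm difference with n per arm is 0.894 × √(2/n).

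- No loss, n = 20: 0.283.
- Baseline and final only, n = 18: 0.298.
- All visits required, n = 29.16/2 = 14.58: 0.331. Simulation gives 0.335 (20,000 trials) and 0.347 (400 trials).
- Mixed model on all available visits: 0.29 to 0.30 by simulation.

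So the gain from a mixed model is about 0.33–0.35 against 0.29–0.30 if all visits enter. It is close to nil (0.298 against about 0.296) if the ANOVA is baseline against final.

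**3. Selective loss in one arm.** Suppose four of 20 Group A patients leave: the two with the poorest week-6 change, then the two with the poorest week-12 change. Simulation gives a spurious benefit to Group A of 0.17 SD (400 trials, Monte Carlo SE about 0.014) or 0.16 SD (larger runs). A closed-form check drops the lowest 20% on week-12 change. The mean of those kept is φ(0.842)/0.8 = 0.280/0.8 = 0.350 SD of change. The week-12 and week-26 changes correlate (1 − 0.6)/0.8 = 0.5. The shift at week 26 is 0.350 × 0.5 × 0.894 = 0.156 SD.

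All four patients lack week 26, so both readings of the ANOVA exclude them and the bias is the same. Against a standard error of 0.894 × √(1/20 + 1/16) = 0.300, it is about half a standard error.

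If leaving is instead driven by a separate symptom score that correlates r with the morphological outcome, the bias shrinks roughly in proportion to r:

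| r | 0 | 0.2 | 0.3 | 0.5 | loss driven by the outcome itself |
|---|---|---|---|---|---|
| bias (SD) | 0.00 | 0.03 | 0.05 | 0.08 | 0.16–0.17 |

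A separate calculation, in SDs of change and with week-12 to week-26 correlation 0.5–0.7, gives 0.05–0.12 for moderate selection and 0.10–0.25 if all the poorest responders leave, at 10–20% dropout. Its top value needs the 0.7 correlation, which is higher than the 0.5 implied above.

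**4. What the mixed model recovers.** In the four-patient scenario its bias is 0.01 SD. That result depends on loss being determined by week-6 and week-12 values of the analysed outcome, and on those values having been collected.

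**The case against.** Several stronger readings are tempting and should not be adopted.

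- A reader might infer that the plan prescribes a completer analysis. It does not say so. Deletion is the default of the named methods combined with silence, and an unstated imputation cannot be ruled out.
- A reader might infer that any missed visit removes a patient. For the ANOVA this holds only if weeks 6 and 12 enter. The visits are not listed, and ultrasound with SFA is described only at the initial and final examinations. Under a baseline-to-final reading, missing week 6 or 12 costs nobody.
- A reader might infer that the paired tests also compare the arms as completers. They are run in each arm separately. The between-arm point rests on the ANOVA, and so on morphology. The paired tests still matter, because they are the only follow-up tests named for VISA-A and NRS and they too lose patients without a final value.
- A reader might take 0.17 SD as the expected bias. It comes from loss fixed by the analysed outcome, in one arm only. Patients are more likely to leave because of pain or inconvenience than because of an ultrasound texture value, so the lower end of the range is at least as plausible for morphology.
- A reader might take the mention of patient tolerance under ESWT application as evidence of differential dropout. It explains the energy range and does not describe patients stopping. Loss of poor responders from Group B would push the bias the other way.

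These points stand, and they limit scope and size. They leave untouched the core: the named methods need complete values and nothing in the plan keeps incomplete patients in.

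**Conclusion.** The concern holds in this limited form. As written, a patient without a week-26 value is lost from the between-arm morphological analysis and from the within-arm paired tests; loss for a missed week 6 or 12 is conditional on those visits entering the ANOVA.

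The size cannot be derived from the document and rests on the assumptions above. At 10% loss per visit, 29 or 36 of 40 patients remain, depending on the reading, and the precision argument for a mixed model carries weight only in the first case. Selective loss in one arm gives a spurious difference of about 0 to 0.17 SD. Confidence is high that the rule is missing, and much lower about how much harm follows. The change should be made, because the risk is real and the remedy nearly free.

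**What to change.** Amend the Data analysis section as follows.

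- Define the analysis population as all randomised patients, analysed in the assigned arm.
- Replace the repeated-measures ANOVA and Friedman test with a linear mixed model (arm, visit, arm-by-visit; unstructured covariance or a patient random effect) fitted to every available visit. Giving up Friedman loses nothing for this question, since it has no between-group factor.
- Name the visits at which each outcome is measured and enters the model.
- Use the same model for VISA-A and NRS, which otherwise have no between-arm follow-up comparison.
- Report arm differences with confidence intervals at week 26, and at week 12 for outcomes measured then.
- State that patients who stop treatment are still invited to the planned visits, and report missing data by arm.
- Keep the complete-case analysis as a sensitivity analysis.

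The cost is a few sentences, no new visits, and some effort to bring back patients who stopped. The model assumes that missingness depends on observed data. If morphology is measured only at baseline and final, the model has little to draw on for those who leave, and obtaining the week-26 measurement matters more than the choice of model.
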